#### 4.4 Pharmacodynamic Endpoints

The PD endpoints include aPTT and FXIc for BMS-986177, aPTT and anti-Xa for heparin and enoxaparin.

[REDACTED]

[REDACTED]

[REDACTED]

[REDACTED]

## 5 SAMPLE SIZE AND POWER

Although the number of patients is not based on statistical power considerations, administration of BMS-986177 to 32 patients with ESRD would provide over 80% probability of observing at

least one occurrence of any AE that would occur with incidence of 5% in the population from which the sample is drawn.

## **6 STUDY PERIODS, TREATMENT REGIMENS AND POPULATIONS FOR ANALYSES**

### **6.1 Study Periods**

- The pre-treatment period will be from the time the Inform Consent Form (ICF) is signed until the day just prior to dosing on Day 1 for all patients. The pre-treatment period should be no longer than 21 days and will include screening, Day -1 to -3, and randomization procedures.
- Period 1 will be from the day of dosing on Day 1 until the day prior to dosing on Day 5, or until study discharge due to premature discontinuation if the patient is not dosed on Day 5.
- Period 2 will be from the day of dosing on Day 5 until the day prior dosing on Day 8, or until study discharge due to premature discontinuation if the patient is not dosed on Day 8.
- Period 3 will be from the day of dosing on Day 8 until the day prior dosing on Day 12, or until study discharge due to premature discontinuation if the patient is not dosed on Day 12.
- Period 4 will be from the day of dosing on Day 12 until the day of study discharge between Day 13 and Day 15 based on last PK sample obtained between 24 to 72 hours post Day 12 dose, or until the day of study discharge due to premature discontinuation after dosing on Day 12.
- If a patient is not discharged between Day 13 and Day 15, any data collected after the day of study discharge will be assigned to the post treatment period.
- Periods 1, 2, 3, and 4 will be considered on-therapy for the purpose of safety analyses.

The definition of each period is included in [Table 6.1-1](#).

**Table 6.1-1 Definition of Period**

PERIOD SEQUENCE	PERIOD NAME	DATE TO BE USED	DEFINITION
1	PRE-TREAT	- CONSENT DATE - DOSE DATE ON DAY 1	Starting with consent date and ending by (<) dose date on Day 1
2	PERIOD 1	- DOSE DATE ON DAY 1 - DOSE DATE ON DAY 5	Starting with dose date on Day 1 and ending by (<) dose date on Day 5
3	PERIOD 2	- DOSE DATE ON DAY 5 - DOSE DATE ON DAY 8	Starting with dose date on Day 5 and ending by (<) dose date on Day 8
4	PERIOD 3	- DOSE DATE ON DAY 8 - DOSE DATE ON DAY 12	Starting with dose date on Day 8 and ending by (<) dose date on Day 12
5	PERIOD 4	- DOSE DATE ON DAY 12 - DISCHARGE DATE	Starting with dose date on Day 12 and ending by ( $\leq$ ) discharge date
6	POST-TREAT	- DISCHARGE DATE	Starting with discharge date + 1

## 6.2 Treatment Regimens

- Treatment A: UFH intravenous infusion.
- Treatment B: BMS-986177 100 mg.
- Treatment C: BMS-986177 300 mg.
- Treatment D: Enoxaparin 40 mg by subcutaneous injection.

## 6.3 Populations for Analyses

- All Enrolled Patients, defined as all patients who signed ICF;
- All Randomized Patients, defined as patients who were randomized to a sequence of treatments including the patients who replace the discontinuing randomized patients;
- Safety Population, defined as all randomized patients who took at least 1 dose of study treatment;
- Pharmacodynamic Population, defined as a subset of the Safety Population and includes all patients who received at least 1 dose of study treatment and had any available PD data;
- Biomarker Population, defined as a subset of the Safety Population and includes all patients who received at least 1 dose of study treatment and had any available post dose biomarker data;
- Pharmacokinetic Population, defined as all patients who received BMS-986177 from whom PK parameter data were obtained before and after HD.

- Evaluable PK Population, defined as a subset of the PK Population and includes all patients who had adequate PK profiles.

## 7 STATISTICAL ANALYSES

SAS® version 9.3 or higher, will be used for statistical analyses, tabulations, and graphical presentations.

### 7.1 General Methods

All data recorded on case report forms will be listed by patient. Descriptive summaries will be presented for continuous variables using number of patients, mean, standard deviation (SD), median, minimum, and maximum. Geometric mean and coefficient of variation (%CV) will also be presented for sample plasma PK parameters, as applicable. Descriptive summaries for categorical variables will utilize counts and percentages.

Where appropriate, baseline is defined as the last non-missing result with a collection date-time less than the date-time of the first dose of study treatment.

Adverse events and medical history will be coded according to the most recent Medical Dictionary for Regulatory Activities version. Previous and concomitant medications will be coded using the BMS Drug Dictionary.

### 7.2 Study Conduct

Deviations from the study protocol, protocol amendments, and administrative changes will be documented. Relevant protocol deviations will be listed.

### 7.3 Study Population

#### 7.3.1 Patient Disposition

Patient disposition will be listed. Summary tables reflecting the number of patients who are enrolled, who are randomized, who are not randomized, and reasons for not being randomized will be presented as overall.

The number of patients who complete the study, who do not complete the study, and reasons for not completing the study, will be summarized for the safety population, as overall and by treatment sequence.

#### 7.3.2 Demographic Characteristics

Demographic characteristics such as gender, age, race, and ethnicity will be listed for the safety population. Demographic characteristics will also be summarized for the safety population, as overall and by treatment sequence.

#### 7.3.3 Physical Measurements

Physical measurements such as body weight, height and body mass index will be listed for the safety population. Measurements will also be summarized by nominal visit and time point for the safety population, as overall and by treatment sequence.

#### **7.3.4 Medical History and Previous Medications**

Medical history and previous medications taken prior to dosing will be listed for the safety population.

#### **7.4 Extent of Exposure**

No analysis regarding extent of exposure is planned. Study treatment administration, randomization schedule, and batch numbers will be documented as per patient listings. Any non-study medications taken by patients, any conducted non-study medical treatment procedures, and any utilized non-study diagnostic procedures will also be listed. Concomitant medications taken during treatment period will be summarized by anatomic class, therapeutic class, generic name, treatment, and overall for the safety population.

#### **7.5 Efficacy**

There are no efficacy assessments in the study.

#### **7.6 Safety**

Analysis of all safety data will follow the BMS guideline of analysis of safety data. The evaluation of safety is based on clinical AEs, vital signs, ECG results, abnormal PE findings, and clinical laboratory results reported during the study.

All data collected from the sampling outside the scheduled visits will only be included in the listing and will be excluded from the summary tables.

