9.2.6 Laboratory Test Result Abnormalities

The following laboratory test result abnormalities should be captured on the nonserious AE CRF page or SAE Report Form electronic, as appropriate. Paper forms are only intended as a back-up option when the electronic system is not functioning.

- Any laboratory test result that is clinically significant or meets the definition of an SAE

- Any laboratory test result abnormality that required the participant to have study treatment discontinued or interrupted
- Any laboratory test result abnormality that required the participant to receive specific corrective therapy

It is expected that wherever possible, the clinical rather than laboratory term would be used by the reporting investigator (eg, anemia versus low hemoglobin value).

Some coagulation tests (eg, aPTT,) are affected by the investigational drug and therefore changes in such tests are not to be considered as AEs but as PD biomarkers.

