#### 4.2 Safety Endpoints

Safety endpoints include incidence of AEs, serious AEs (SAEs), AEs leading to discontinuation, and death as well as marked abnormalities in clinical laboratory tests, ECGs, vital sign measurements, and PEs.

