##### **7.6.3 Adverse Events**

Adverse events which occur on or after the first dose of study treatment will be tabulated. Events will be assigned to the last study treatment administered at the time of onset. Events occurring after discharge will be assigned to the last study treatment received. The proportion of patients having an AE will be calculated as the number of patients having the event in the specific treatment interval, divided by the total number of patients receiving study treatment during that treatment interval.

All AE listings will indicate the unique patient identifier, age, gender, current treatment, date of onset, date of resolution, day of onset relative to the start of treatment, action taken, investigator's assessment of severity, and relationship to study treatment. Additional listings will be provided for AEs leading to discontinuation and AEs without recorded resolution.

All AEs will be summarized by system organ class (SOC), preferred term (PT), treatment, and overall for the safety population. Summaries of AEs will include AEs, AEs by intensity, AEs related to study treatment, and AEs leading to discontinuation.

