#### **7.6.4 Clinical Laboratory Evaluations**

The results of all protocol-specified clinical laboratory tests will be listed by patient for the safety population. Laboratory measurements and corresponding change from baseline values will be summarized by treatment and scheduled nominal visit for each laboratory test.

Laboratory evaluations will be reported both in conventional units and in SI units.

Laboratory results will be classified as markedly abnormal based on sponsor defined criteria. The criteria used for classifying laboratory test results as markedly abnormal will be listed. Laboratory results for patients with any marked laboratory abnormality (scheduled and unscheduled) will be listed. This listing will include all observations for the specific laboratory test and patient, not only the marked laboratory abnormality measurements. The frequency of patients with any marked laboratory abnormality, based on pre-specified criteria, will be presented.

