## **8 CONTENT OF REPORTS**

Statistical components for the CSR will be based on the content of this statistical analysis plan. Details of the tables, listings, and figures to be prepared for the final CSR will be included in a study-specific Data Presentation Plan.

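### Read literally, the SAP leaves a marked laboratory abnormality seen only on a sample from outside a scheduled visit out of the frequency count

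*SAP*

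**What the plan says.** SAP 7.6 opens the safety section with a general rule: "All data collected from the sampling outside the scheduled visits will only be included in the listing and will be excluded from the summary tables". It states no exception.

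SAP 7.6.4 then treats marked laboratory abnormalities in two places. For the listing: "Laboratory results for patients with any marked laboratory abnormality (scheduled and unscheduled) will be listed". For the count: "The frequency of patients with any marked laboratory abnormality, based on pre-specified criteria, will be presented". The second sentence does not say whether unscheduled results are included. The same section ties the summaries of laboratory values and changes to scheduled nominal visits.

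SAP 4.2 makes the count matter. It names the incidence of adverse events among the safety endpoints, "as well as marked abnormalities in clinical laboratory tests, ECGs, vital sign measurements, and PEs". Clinical laboratory values are also among the primary endpoints in Protocol Table 4.-1.

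SAP 7.6 says that safety analysis follows a sponsor guideline. SAP 8 adds: "Details of the tables, listings, and figures to be prepared for the final CSR will be included in a study-specific Data Presentation Plan". Neither of those papers is among the documents.

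**The concern.** A tabulated frequency of patients is, in ordinary usage, a summary table, so the general rule in 7.6 appears to reach it. Unscheduled results are named in the listing sentence of 7.6.4 and not in the frequency sentence, which fits that reading. The by-visit laboratory summaries are already restricted to scheduled visits by 7.6.4 itself, so for laboratory data the marked-abnormality count is the main place where the rule in 7.6 would change a result.

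Samples from outside scheduled visits are often taken because something looked wrong. If they are left out, the table can show fewer patients with a marked abnormality than the listing does. Two programmers working from this SAP could produce different counts for a named safety endpoint.

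**Working it through.** **The plan's own figure.** Protocol 10.1 and SAP 5 state over 80% probability of seeing at least one event of 5% incidence in 32 patients. 1 − 0.95^32 = 0.806, so the figure reproduces. The point here rests on the text and not on this figure, but the same formula shows scale.

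**The two readings.**

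| Patient's marked abnormality | Listing (7.6.4) | Count, with 7.6 applied literally | Count, with *any* in 7.6.4 taken as decisive |
|---|---|---|---|
| On a scheduled sample | yes | yes | yes |
| Only on a sample from outside a scheduled visit | yes | no | yes |

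The readings differ only in the second row. Against a count over all samples, the literal count can be equal or lower, never higher.

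**One patient, for illustration.** Inputs: 32 participants, with 24 expected to complete all four treatments (Protocol 5.2). Exact 95% (Clopper-Pearson) limits:
- For 0/n, the upper limit is 1 − 0.025^(1/n).
- For 1/n, the lower limit is 1 − 0.975^(1/n), and the upper limit solves (1−p)^n + n·p·(1−p)^(n−1) = 0.025.

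| n | Patient counted | Patient not counted |
|---|---|---|
| 32 | 1/32 = 3.1% (0.1% to 16.2%) | 0/32 (0% to 10.9%) |
| 24 | 1/24 = 4.2% (0.1% to 21.1%) | 0/24 (0% to 14.2%) |

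**Chance that the table shows any case.** Take a marked abnormality with 5% incidence (the plan's figure for adverse events, borrowed here). Let q be the share of affected patients whose abnormality appears only outside scheduled visits. The documents give no value for q; 0.10 to 0.50 is an assumed range. The chance is 1 − (1 − 0.05(1−q))^n.

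| q | n = 32 | n = 24 | Expected patients in table, n = 32 |
|---|---|---|---|
| 0 (all counted) | 80.6% | 70.8% | 1.60 |
| 0.10 | 77.1% | 66.9% | 1.44 |
| 0.25 | 70.6% | 60.0% | 1.20 |
| 0.50 | 55.5% | 45.5% | 0.80 |

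**How an added result would be attributed.** For adverse events, SAP 7.6.3 uses time of onset: "Events will be assigned to the last study treatment administered at the time of onset". SAP Table 6.1-1 uses dates only; Period 1, for example, is defined as "Starting with dose date on Day 1 and ending by (<) dose date on Day 5". Under the table, a sample drawn on Day 5, 8 or 12 before dosing would fall to the treatment about to be given. Attribution by date-time avoids this.

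**The case against.** **The specific text may already include these results.** In 7.6.4 the listing sentence speaks of any marked abnormality and spells out both kinds of result; the frequency sentence, soon after, again says *any*. Only the by-visit summaries are limited to scheduled visits. One can fairly read 7.6 as governing by-visit tables and 7.6.4 as counting everything. The sponsor guideline or the Data Presentation Plan may say so. This stands, and it is why the finding is an ambiguity and not a proven undercount.

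**A scheduled-only count is legitimate.** It uses the same sampling schedule for every treatment, whereas extra samples may be drawn unequally. Some could also follow the mid-week standard-of-care dialysis (Days 3 and 10 in the design schematic) and would still be attributed to the preceding study treatment. This stands too, and it is the reason to show both counts.

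**Little is lost.** The listing shows all observations for the patient and test concerned. Protocol 9.2.6 sends to adverse event reporting "Any laboratory test result that is clinically significant or meets the definition of an SAE", and adverse events are tabulated. This largely stands. The one gap is that 9.2.6 treats drug-affected coagulation tests such as aPTT as pharmacodynamic markers and not as adverse events.

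**Stronger readings that the documents do not support.** A reader might infer that every extra draw on a dosing day is excluded. SAP 7.6 speaks of sampling outside scheduled visits, and Days 1, 5, 8 and 12 are scheduled visits, so a repeat draw on one of them is not plainly caught. A reader might then infer that the exclusion falls mainly on BMS-986177 days, because patients stay longer in the facility. Those hours belong to scheduled dosing visits, and hours of stay are not numbers of samples, so they do not measure what the rule removes.

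**Conclusion.** The point holds as a minor ambiguity. SAP 7.6 states an exclusion without exception, the frequency sentence in 7.6.4 does not override it, and a programmer following the text could leave a patient out of the count for a named safety endpoint. The opposite reading is possible.

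The conclusion assumes that the frequency presentation is a summary table in the sense of 7.6, and that no unseen sponsor paper resolves the conflict. The effect is confined to this table. Each uncounted patient is worth 3.1 percentage points at n = 32 or 4.2 at n = 24. How many patients would be affected, if any, cannot be told from the documents.

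A reader might also infer that the laboratory and ECG analysis is deficient for lacking within-patient differences between treatments. The documents do not support calling that an error: no hypothesis is formally tested, and Protocol 10.3.2 plans descriptive summaries by treatment and time point, which the SAP carries out.

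**What to change.** Before database lock, amend SAP 7.6 to this effect: *Results sampled outside scheduled visits are left out of by-visit summaries only. They count towards the frequency of patients with marked laboratory abnormalities and are attributed, by collection date-time, to the study treatment most recently given before the sample.* Refer to this rule in 7.6.4.

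Show the scheduled-only count beside the full count, because sampling outside scheduled visits may differ between treatments and some samples may follow the mid-week dialysis.

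The cost is one sentence and one extra column; no new samples or visits are needed. The downside is that the full counts may be slightly higher and may partly reflect unequal sampling, which the second column makes visible.

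While the laboratory text is open, one further pair of passages should be reconciled. The laboratory row of Protocol Table 2.-2 refers to a draw before Day 1 and to draws 3 to 6 hours after dialysis; Protocol 5.1 and SAP 2.1 place clinical biochemistry before dosing. Nothing in the point above depends on the answer.

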##### **7.6.1 Deaths**

All reported deaths after a patient is enrolled (ie, has signed the ICF) will be listed by patient.

##### **7.6.2 Serious Adverse Events**

All reported SAEs will be listed for all enrolled patients and will be summarized for the safety population.

##### **7.6.3 Adverse Events**

Adverse events which occur on or after the first dose of study treatment will be tabulated. Events will be assigned to the last study treatment administered at the time of onset. Events occurring after discharge will be assigned to the last study treatment received. The proportion of patients having an AE will be calculated as the number of patients having the event in the specific treatment interval, divided by the total number of patients receiving study treatment during that treatment interval.

All AE listings will indicate the unique patient identifier, age, gender, current treatment, date of onset, date of resolution, day of onset relative to the start of treatment, action taken, investigator's assessment of severity, and relationship to study treatment. Additional listings will be provided for AEs leading to discontinuation and AEs without recorded resolution.

All AEs will be summarized by system organ class (SOC), preferred term (PT), treatment, and overall for the safety population. Summaries of AEs will include AEs, AEs by intensity, AEs related to study treatment, and AEs leading to discontinuation.

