#### AE Counting Rules:

Where a patient has the same AE, based on PT, reported multiple times in a single analysis period, the patient will only be counted once at the PT level in AE frequency tables.

Where a patient has multiple AEs within the same SOC in a single analysis period, the patient will only be counted once at the SOC level in AE frequency tables.

When a patient has the same AE, based on PT, reported multiple times in a single analysis period, the following criteria, in order of precedence, will be used to select the event to be included in summary tables:

- Relationship to study treatment
- Intensity of event
- Onset date and time

When reporting AEs by intensity, in addition to providing a summary table based on the event selection criteria detailed above, summary tables will also be provided based on the most intense event during the analysis period - independent of relationship to study treatment. For these tables, the following criteria, in order of precedence, will be used to select the event to be included in summary tables:

- Intensity of event
- Onset date and time

Patients will only be counted once in the 'Total' at their maximum intensity, regardless of SOC or PT.

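### Does counting post-discharge events under the last treatment received distort the by-treatment safety tables?

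*SAP*

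**What the plan says.** SAP 7.6.3 tabulates adverse events (AEs) from first dose onward and assigns each to the last treatment given at onset. It then adds: "Events occurring after discharge will be assigned to the last study treatment received". The numerator is patients with the event in the treatment interval, "divided by the total number of patients receiving study treatment during that treatment interval". The display is by treatment: "All AEs will be summarized by system organ class (SOC), preferred term (PT), treatment, and overall for the safety population". For SAEs, SAP 7.6.2 says only: "All reported SAEs will be listed for all enrolled patients and will be summarized for the safety population". It does not ask for that summary by treatment.

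SAP 6.1 states: "Periods 1, 2, 3, and 4 will be considered on-therapy for the purpose of safety analyses". Table 6.1-1 ends Period 4 on the discharge date and defines the post-treatment period as "Starting with discharge date + 1". The counting rules in 7.6.3 apply to an event "reported multiple times in a single analysis period". The SAP defines neither *treatment interval* nor *analysis period*. SAP 7.6 refers to a sponsor guideline on safety analysis, which is not among the documents.

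Protocol 9.2.1 requires SAEs to be collected up to 30 days after dosing stops. In Protocol Table 2.-2, nonserious AE monitoring ends at the Day 13-15 visit.

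**The concern.** AEs are the primary endpoint. Read together, the rules let a single-dose treatment column take in about four weeks of follow-up that the SAP itself does not call on-therapy. By then patients are back on standard of care (Protocol 7.8), which Protocol 8.1 identifies as unfractionated heparin (UFH). Protocol 6.1 puts five half-lives of BMS-986177 at 2 days, so a late event is unlikely to reflect the dose. A bleeding SAE three weeks after discharge, during routine heparin dialysis, could still count under BMS-986177.

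Numerator and denominator also fit poorly. Without dropout, only 8 of the 32 patients behind each column supply post-discharge time, yet all 32 form the denominator. If early stopping clustered after one treatment, that column would collect more follow-up than the others, and a background rate could pass for a treatment difference.

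**Working it through.** The documents give no figure on this point. The one probability in the SAP (section 5, over 80%) reproduces as 1 - 0.95^32 = 0.806 but does not bear on it.

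**Inputs.** From Table 6.1-1, Periods 1, 2 and 3 last 4, 3 and 4 dates; Period 4 runs from Day 12 through discharge on Day 13-15, so 2-4 dates. The SAE window closes on Day 12 + 30 = Day 42. Days 12-42 are 31 dates, which leaves 29-27 after discharge. There are 32 patients (Protocol 5.2) allocated 1:1:1:1 (SAP 2.2), so 8 per sequence. In SAP Table 2.1-1 each treatment appears once in each period.

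**Share of eligible time per treatment, all completing.**
- Total: 8 × (4 + 3 + 4 + 31) = 336 patient-days.
- After discharge: 8 × 27 = 216 to 8 × 29 = 232.
- Share: 216/336 = 64.3% to 232/336 = 69.0%, the same for all four treatments.

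Other day-counting conventions give 63-71%. With 8 dropouts spread evenly over the sequences, the share is 66-74%, again equal across treatments.

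**Effect on an SAE percentage.** Assume a constant background hazard with 30-day risk p: r = -ln(1 - p)/30 and f(d) = 1 - exp(-r·d). The values of p are assumptions.
- With post-discharge events: [f(4) + f(3) + f(4) + f(31)]/4.
- Periods 1-4 only: [f(4) + f(3) + f(4) + f(2 to 4)]/4.

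| p | With post-discharge | Periods 1-4 only | Patients of 32 | Difference |
|---|---|---|---|---|
| 5% | 1.8% | 0.6% | 0.56 vs 0.18-0.20 | 0.36-0.38 |
| 10% | 3.5% | 1.1-1.3% | 1.13 vs 0.36-0.42 | 0.71-0.77 |
| 20% | 7.2% | 2.4-2.8% | 2.29 vs 0.76-0.88 | 1.41-1.53 |

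The ratio is 2.6-3.2. It applies to a by-treatment SAE percentage, which SAP 7.6.2 does not specify.

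**Effect on the table the SAP does specify.** In the all-AE table, SAEs are pooled with nonserious events. Let q be the assumed on-therapy any-AE risk per period. One quarter of patients add post-discharge SAE risk of about f(27) = 0.09 at p = 10%, so the any-AE percentage becomes q + 0.25 × (1 - q) × 0.09:
- q = 10%: 12.0%, ratio 1.20
- q = 20%: 21.8%, ratio 1.09
- q = 40%: 41.4%, ratio 1.03

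**Extreme dropout (assumed).** Protocol 5.2 allows for 8 non-completers. Suppose all 8 stop straight after 300 mg: 3 in sequence 1, 2 in sequence 3 and 3 in sequence 4. At p = 10%:
- 300 mg: [16 f(31) + 11 f(4) + 5 f(3)]/32 = 1.86/32 = 5.8%.
- UFH: 0.80/27 = 3.0%.
- 100 mg: 0.88/27 = 3.3%.
- Enoxaparin: 0.79/27 = 2.9%.

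At the other treatments' 2.9-3.3%, 300 mg would show about 0.9-1.1 patients of 32. The excess is therefore about one patient, even here.

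**The case for a change.** The strongest opposing case is that the percentage describes neither a single-dose period nor a 30-day follow-up, that the text does not settle whether post-treatment events enter the columns, and that defining this before database lock would cost only wording and one table block. The arithmetic behind it is right, and the two undefined terms are a real omission. Four things limit what follows.

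- **The rules do not contradict each other.** SAP 6.1 labels periods; it does not bar post-treatment events from tables. SAP 7.6.3 says where such events go. The natural reading of *treatment interval* is from one dose to the next, with the last interval running on under the post-discharge rule.
- **The threefold ratio assumes equal detection.** No contact is scheduled after Day 13-15, and Protocol 9.2.1 does not oblige investigators to seek events in former participants. The 30-day window still applies, but 64-69% is eligible calendar time rather than comparable observation.
- **Periods 1-4 are not a clean boundary either.** The midweek session, on Days 3 and 10, is run on standard of care (SAP 2.1) and lies inside Periods 1 and 3. Restricting columns to those periods would not remove events under routine anticoagulation.
- **The alternative display has its own defect.** Suppose late events move to a separate block but related ones stay under the last treatment. A related SAE could then appear in the related-AE table and be missing from the main AE table. If related ones move too, a delayed drug effect leaves its treatment column. The separate block would also rest on about 8 patients per treatment.

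Table 6.1-1 ends Periods 1-3 only at the next dose date, which an early stopper never reaches. The SAP 6.1 text already covers this, for Period 1 with "or until study discharge due to premature discontinuation if the patient is not dosed on Day 5" and likewise for Periods 2 and 3.

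**Conclusion.** No change is needed. Assigning late events to the last treatment is a pre-specified choice that keeps every SAE in view under some treatment. Statisticians may reasonably prefer a split display, but this is descriptive safety reporting with no hypothesis to test. With full completion or balanced dropout, the rule raises all four columns equally and leaves comparisons between treatments intact. The absolute effect is under one patient of 32 per treatment at assumed background risks of 5-10%, and about one and a half at 20%. A false difference needs early stopping to cluster after one treatment; the most extreme assumed case yields about one patient at 10% risk.

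SAP 7.6.3 requires listings with current treatment, onset date, onset day and relationship, so anyone reading an SAE count this small can see which events came after discharge. The undefined terms can be resolved from Table 6.1-1 and the assignment rule when the tables are laid out in the Data Presentation Plan (SAP 8).

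The conclusion rests on assumed background risks, a constant hazard and a window closing on Day 42. The sponsor guideline could not be checked and may already define the terms.
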